5.5.3 Treatment compliance

At all times, when dispensing study drug, research center personnel will review the instructions, printed on the packaging, with subjects. Subjects will be asked to maintain a diary to record the drug administration. Subjects will be asked to bring any unused study drug and empty study drug containers to the research center at their next visit. Research personnel will count and record the number of used and unused study drug capsules at each visit and reconcile with the subject diary.

5.6 Concomitant therapy

5.6.1 Recommended concomitant therapy

Subjects should receive full supportive care, including transfusions of blood and blood products, antibiotics, and antiemetics when appropriate.

5.6.1.2 Anti-coagulation Consideration

Pomalidomide increases the risk of thrombotic events in subjects who are at high risk or with a history a thrombosis, in particular when combined with other drugs known to cause thrombosis.

Subjects will take aspirin 325 mg/day to prevent venous thrombosis while on pomalidomide. Low molecular weight heparin may be utilized in subjects that are intolerant to ASA. Coumadin should be used with caution and close monitoring of INR.

5.6.2 Prohibited concomitant therapies

Concomitant use of sargramostim (GM-CSF), other anti-cancer therapies, including radiation, thalidomide, or other investigational agents is not permitted while subjects are

Pomalidomide

receiving study drug during the treatment phase of the study. G-CSF is not allowed during Phase I, Cycle 1 while evaluating for DLT. However, G-CSF is allowed for Phase II participants or following cycle 1 for Phase I participants.

5.7 Discontinuation of Study-Treatment

Treatment will continue until the occurrence of any of the following events.

- Disease progression
- Adverse event(s) that, in the judgment of the Investigator, may cause severe or permanent harm or which rule out continuation of the treatment regimen.
- Major violation of the study protocol.
- Withdrawal of consent
- Lost to follow up
- Death
- Suspected pregnancy

5.8 Follow-Up

Subjects who discontinue treatment for any reason, will be followed every 3 months until disease progression, then annually for survival, as clinically indicated. At treatment discontinuation, subjects will undergo a safety assessment approximately 30 days post the last dose of study drug. In addition off study evaluations per the Schedule of Assessments, Section 2 will be done.

6 Adverse events

6.1 Serious Adverse Event (SAE) Definition

A serious adverse event is one that at any dose (including overdose):

- Results in death
- Is life-threatening¹
- Requires in-patient hospitalization or prolongation of existing hospitalization
- Results in persistent or significant disability or incapacity²
- Is a congenital anomaly or birth defect
- Is an important medical event³

Suspected positive Pregnancy

¹"Life-threatening" means that the subject was at immediate risk of death at the time of the serious adverse event; it does not refer to a serious adverse event that hypothetically might have caused death if it were more severe.

²"Persistent or significant disability or incapacity" means that there is a substantial disruption of a person's ability to carry out normal life functions.

³Medical and scientific judgment should be exercised in deciding whether expedited reporting is appropriate in situations where none of the outcomes listed above occurred. Important medical events that may not be immediately life-threatening or result in death or hospitalization but may jeopardize the subject or may require intervention to prevent one of the other outcomes listed in the definition above should also usually be considered serious. Examples of such events include allergic bronchospasm requiring intensive treatment in an emergency room or at home, blood dyscrasias or convulsions that do not result in in-patient hospitalization, or the development of drug dependency or drug abuse. A new diagnosis of cancer during the course of a treatment should be considered as medically important.

6.2 Adverse Drug Reaction Reporting

Toxicity will be scored using CTCAE Version 4.0 for toxicity and adverse event reporting. A copy of the CTCAE Version 4.0 can be downloaded from the CTEP homepage (HTTP://CTEP.INFO.NIH.GOV). All appropriate treatment areas should have access to a copy of the CTCAE Version 4.0. All adverse clinical experiences, whether observed by the investigator or reported by the subject, must be recorded, with details about the duration and intensity of each episode, the action taken with respect to the test drug, and the subject's outcome. The investigator must evaluate each adverse experience for its relationship to the test drug and for its seriousness.

The investigator must appraise all abnormal laboratory results for their clinical significance. If any abnormal laboratory result is considered clinically significant, the investigator must provide details about the action taken with respect to the test drug and about the subject's outcome.

AEs and SAEs will be reported from the first dose of study drug through 30 days after administration of the last dose of study drug or the start of subsequent therapy for amyloidosis, whichever occurs first. All SAEs should continue to be monitored until they are resolved or are clearly determined to be due to a patient's stable or chronic condition or intercurrent illness(es).

Pregnancies

Pregnancies occurring while the subject is on pomalidomide or within 4 weeks after the subject's last dose of pomalidomide are considered expedited reportable events. If the subject is on pomalidomide, it is to be discontinued immediately and the subject is to be instructed to return any unused portion of pomalidomide to the Investigator. The pregnancy must be reported to Celgene Corporation Worldwide Drug Safety Surveillance (WWDSS) within 24 hours of the Investigator's knowledge of the pregnancy by phone and facsimile using the SAE Form.

Pomalidomide

The Investigator will follow the subject until completion of the pregnancy, and must notify Celgene Corporation Worldwide Drug Safety Surveillance (WWDSS) of the outcome as specified below. The Investigator will provide this information as a follow-up to the initial SAE.

6.3 Investigator Reporting Responsibilities

The conduct of the study will comply with all FDA safety reporting requirements.

IND Annual Reports

If the FDA has granted an IND number, it is a requirement of 21 CFR 312.33, that an annual report is provided to the FDA within 60-days of the IND anniversary date. 21 CRF 312.33 provides the data elements that are to be submitted in the report. The Annual Report should

be filed in the study's Regulatory Binder, and a copy provided to Celgene Corporation as a supporter of this study as follows.

Celgene Corporation Attn: Medical Development [name] [contact]

All adverse experience reports must include the subject number, age, sex, weight, severity of reaction (mild, moderate, severe), relationship to study drug (probably related, unknown relationship, definitely not related), date and time of administration of test medications and all concomitant medications, and medical treatment provided. The investigator is responsible for evaluating all adverse events to determine whether criteria for "serious" and as defined above are present. The investigator is responsible for reporting adverse events to Celgene as described below.

6.3.1 Expedited reporting by investigator to Celgene

Expedited reporting by investigator to Celgene

Serious adverse events (SAE) are defined above. The investigator must inform Celgene in writing using a Celgene SAE form or MEDWATCH 3500A form of any SAE within 24 hours of being aware of the event. The written report must be completed and supplied to Celgene by facsimile within 24 hours/1 business day. The initial report must be as complete as possible, including an assessment of the causal relationship between the event and the investigational product(s), if available. Information not available at the time of the initial report (e.g., an end date for the adverse event or laboratory values received after the report) must be documented on a follow-up report. A final report to document resolution of the SAE is required. The Celgene tracking number (PO-AMYL-PI-0024) and the institutional protocol number should be included on SAE reports (or on the fax cover letter) sent to Celgene. A copy of the fax transmission confirmation of the SAE report to Celgene should be attached to the SAE and retained with the patient records.

Report of Adverse Events to the Institutional Review Board

The principal Investigator is required to notify his/her Institutional Review Board (IRB) of a serious adverse event according to institutional policy.

6.3.2 Investigator Reporting to the FDA

Adverse drug reactions that are **Serious**, **Unlisted/unexpected**, **and at least possibly associated to the drug**, and that have not previously been reported in the Investigators brochure, or reference safety information document should be reported promptly to the Food and Drug Administration (FDA) in writing by each investigator/physician engaged in clinical research. A clear description of the suspected reaction should be provided along with an assessment as to whether the event is drug or disease related.

The investigator/physician shall notify the FDA by telephone or by fax of any unexpected fatal or life threatening experience associated with the use of the drug. As soon as possible, but no later than 7 calendar days after the sponsors initial receipt of the information. Each

Poma	lidon	ahin
i una	nuon	nue

phone call or fax shall be transmitted to the FDA new drug review division in the Center for Drug Evaluation and Research or the product review division in the Center for Biologics Evaluation and Research that has responsibility for review of the IND if applicable.

6.4 Adverse event updates/IND safety reports

Celgene shall notify the Investigator via an IND Safety Report of the following information:

- Any AE associated with the use of study drug in this study or in other studies that is both serious and unexpected.
- Any finding from tests in laboratory animals that suggests a significant risk for human subjects including reports of mutagenicity, teratogenicity, or carcinogenicity.

The Investigator shall notify his/her IRB/EC promptly of these new serious and unexpected AE(s) or significant risks to subjects.

The Investigator must keep copies of all AE information, including correspondence with Celgene and the IRB/EC, on file (see Section 11.4 for records retention information).

7 Response-Criteria

Efficacy assessments are scheduled to occur every three months while on therapy.

- 7.1 Hematologic Response Criteria
- **CR** Negative serum and urine immunofixation electrophoresis, normal serum free light chain ratio
- **VGPR** dFLC <40 mg/L, dFLC = difference in involved and uninvolved serum free lightchain levels
- **PR** dFLC reduction >50%, dFLC = difference in involved and uninvolved serum free light-chain levels
- **SD** Meets neither criteria for CR, VGPR, PR or PD
- **PD** From CR, an increase in serum M-protein to > 0.5 g/dL, an increase in the urine M-protein to > 200 mg/day, or an increase in the serum monoclonal free light chain by > 10 mg/dL (100 mg/L). From VGPR, PR or SD, an increase in the serum M-protein from the lowest level by > 50%, as long as the absolute magnitude of this increase is > 0.5 g/dL; or an increase in the urine M-protein from the lowest level by 50%, as long as the absolute magnitude of this increase is > 200 mg/day; or an increase in the serum or urine monoclonal free light chain by > 50% from the lowest level, as long as the absolute magnitude is > 10 mg/dL (100 mg/L).

Measurable disease to enter on the clinical trial

dFLC of 50 mg/L, dFLC = difference in involved and uninvolved serum free light levels

7.2 Organ Response-Criteria:

A subject will be said to have had an organ response in an involved organ if *any* of the following criteria are met, and none of the criteria in Section 10.4 are met.

Kidney: 50% reduction in 24-hour urine protein excretion in the absence of progressive renal insufficiency (defined as a 25% increase in serum creatinine, as long as that is \geq to an absolute increase of 0.5 mg/dL). In the case of nephrotic syndrome: a decrease in proteinuria to < 1g/24h and an improvement in one of 2 extrarenal features – normalization of serum albumin or resolution of edema and/or discontinuation of diuretics in response to improvement in edema.

Heart: $\geq 2 \text{ mm}$ reduction in the interventricular septal (IVS) thickness by echocardiogram, improvement of ejection fraction by $\geq 20\%$ (echocardiogram must be performed at the same institution), or decrease in 2 NYHA classes without increase in diuretic need (see Appendix E for class definitions).

Liver: \geq 50% decrease in normalization of an initially elevated alkaline phosphatase level or reduction in the size of the liver by at least 3 cm (determined by US or CT).

Neuropathy: While neurotoxicity is acceptable for determining organ involvement, it will not be adequate for assessing organ response; organ response will be indeterminable for subjects in which neurotoxicity is the only site of organ involvement.

Gastrointestinal Tract: While GI involvement is acceptable for determining organ involvement, it will not be adequate for assessing organ response: organ response will be indeterminable for subjects in which GI is the only site of organ involvement.

8 **Protocol Amendments/Deviations**

8.1 Protocol amendments

Any amendment to this protocol must be agreed to by the Principal Investigator and reviewed and approved by Celgene. Amendments should only be submitted to IRB/EC after consideration of Celgene review. Written verification of IRB approval will be obtained before any amendment is implemented.

8.2 **Protocol deviations**

When an emergency occurs that requires a deviation from the protocol for a subject, a deviation will be made only for that subject. A decision will be made as soon as possible to determine whether or not the subject (for whom the deviation from protocol was effected) is to continue in the study. The subject's medical records will completely describe the deviation from the protocol and state the reasons for such deviation. In addition, the Investigator will notify the IRB in writing of such deviation from protocol.

Non-emergency minor deviations from the protocol will be permitted with approval of the Principal Investigator.

9 Data Management

9.1 Analyses and Reporting

Data will be analyzed and reported after study is completed or meaningful endpoints are reached. All subsequent data collected will be analyzed and reported in a follow-up clinical report.

9.2 Data Monitoring Committee

Toxicity and accrual monitoring will be performed on a routine basis by the study investigators as well as the multidisciplinary members of the Amyloid Treatment and Research Program at Boston University, which has over 40 years' experience in the treatment of AL amyloidosis. Subjects will undergo toxicity assessment, performance status assessment and laboratory tests before beginning each new cycle. Response assessment will be conducted every three cycles. The clinical status and laboratory reports of the study participants will be reviewed routinely by the co-investigators at the weekly meetings of the Stem Cell Transplant Program and reviewed by the Amyloid Program at weekly meetings. Dose modifications/interruptions or discontinuation will be implemented according to Section 5.5.

In addition, the BMC Cancer Center's Internal Data and Safety Monitoring Committee (DSMC) will review the protocol, and will determine review frequency based on level of risk. The protocol will be reviewed at least annually by the DSMC. Please see full DSMB Charter in Appendix 4.

9.3 Study monitoring and auditing

9.3.1 Investigator responsibilities

Investigator responsibilities are set out in the ICH guideline for Good Clinical Practice (GCP) and in the US Code of Federal Regulations.

Investigators must enter study data onto CRFs or other data collection system. The Investigator will permit study-related monitoring visits and audits by Celgene or its representatives, IRB/EC review, and regulatory inspection(s) (e.g., FDA, EMEA, TPP), providing direct access to the facilities where the study took place, to source documents, to CRFs, and to all other study documents.

The Investigator, or a designated member of the Investigator's staff, must be available at some time during monitoring visits to review data and resolve any queries and to allow direct access to the subject's records (e.g., medical records, office charts, hospital charts, and study related charts) for source data verification. The data collection must be completed prior to each visit and be made available to the Celgene representative so that the accuracy and completeness may be checked.

10 Statistical Plan

10.1 Overview

This is a Phase I/II study. Responses and toxicity will be compared informally to those reported lenalidomide and dexamethasone combined.

The Phase I portion of the study will be aimed at determining the safety profile and the MTD of pomalidomide. A 3+3 dose escalation scheme will be implemented. Subjects will receive escalating doses of pomalidomide orally on D1-21 in a 28-day cycle in the absence of disease progression or unacceptable toxicity.* Pomalidomide has been safely given to persons with relapsed/refractory myeloma subjects at 2 mg/day continuously in a small Phase II study. Therefore, the estimated safe starting dose of pomalidomide will be 2 mg/day continuously. DLTs will be assessed in Cycle 1 only. Dose escalation of pomalidomide will continue until MTD has been identified or a maximum planned dose (4 mg/day continuously) is determined to be safe.

^{*} Pomalidomide dosing for Phase I cohorts 1 and 2 given on days 1-28 of a 28-day cycle and changed to Days 1-21 of a 28 day cycle with Cohort 3.

10.2 Datasets to be analyzed

Data for safety analysis will be obtained utilizing the NCI Common Terminology Criteria for Adverse Events v4.0.

DLT Based on the first cycle; toxicity considered by the investigator to be related to pomalidomide; Grade 4 thrombocytopenia or neutropenia; \geq Grade 3 non-hematologic toxicity

MTD The dose level at which DLT occurs in no more than 1 of 6 subjects (ie, the dose level below that at which DLT was established).

Data to be included in the analysis for the hematologic response endpoint include evaluation of serum free light chain assay, monoclonal protein in serum or urine by immunofixation electrophoresis, percentage of plasma cells and presence of clonal dominance of kappa or lambda isotope on bone marrow biopsy.

Data for the secondary endpoint of organ response will include creatinine and 24 hour urine protein, liver span and liver function tests, mean left ventricular wall thickness, NYHA heart failure class, orthostatic vital signs and symptoms, GI symptoms and evaluation of peripheral neuropathy.

Data for the exploratory endpoint include BNP and troponin I levels.

10.3 Statistical Methodology

Determination of Sample Size

Based on the dose escalation scheme, as many as 30 subjects may be enrolled in this study.

The number of subjects enrolled will depend on the outcome of the actual dose escalation process. The dose-escalation phase consists of 3 cohorts, each with 2 to 6 subjects enrolled depending on when DLT occurs. Therefore, a minimum of 2 and a maximum of 18 subjects will be enrolled in this phase.

An additional 12 subjects will be enrolled in an expanded cohort for efficacy at each schedule. Therefore, an additional 12 subjects could potentially be enrolled.

It is expected that approximately 30 patients will be enrolled in the phase I/II portions of this study. The endpoints measured in the protocol will be overall response rate (ORR) determined by either CR, VGPR or PR and response of one or more organs. It is estimated by the principle investigator's approximate frequency of response in 18 patients (6 patients will be dosed at the MTD during the phase I portion of this trial plus the additional 12 patients at this MTD dose during the phase II portion). Using the adjusted Wald's confidence interval for the proportion and the corresponding point estimates for hypothetical data, it is expected that if 6 out of 18 have ORR then the estimated response rate would be 35.57% with a 90% confidence interval between 18.21% and 52.81% with similar estimates for organ response.

Randomization and Stratification This is not a randomized study.

Populations for Analysis

The safety population will include all subjects who received at least 1 dose of study drug.

The additional 12 subjects enrolled in the expanded cohort for efficacy will comprise the efficacy population.

Procedures for Handling Missing, Unused, and Spurious Data

No imputation of values for missing data will be performed. Standard clinical monitoring and data management practices will be used to ensure the integrity of data.

General Methodology

In general, summary tabulations will be presented by dose group showing the number of observations, mean, standard deviation, median, minimum, and maximum for continuous variables, and the number and percent (calculated using non-missing values) per category for categorical data.

Safety Analysis

• Determination of MTD

The determination of MTD will be achieved by the results of a deterministic algorithm; thus, statistical hypothesis testing is not intended.

The evaluation of MTD will be based on data from subjects who receive pomalidomide and whose data are interpretable in the context of study drug-specific toxicity (ie, subjects should have had sufficient safety assessments performed to determine whether DLT occurred and should not have received alternate antineoplastic therapies through cycle 1). Subjects who are withdrawn from the study for reasons other than DLT before completing cycle 1 and are replaced consequently will not be included in the analysis of MTD. Subjects will be analyzed according to the dose actually received.

Pharmacokinetics/Pharmacodynamics Not applicable.

Efficacy Analysis

The efficacy analysis will be based on confirmed hematological response and confirmed organ response. The analysis of response data at the MTD will be descriptive, consisting of 2-sided 90% confidence intervals.

Additional analyses of efficacy data at the MTD will consist of evaluations of time to hematologic response, duration of hematologic response, and time to worsening of hematologic and/or organ function. These analyses will also be descriptive in nature.

Analysis of the rates of responders for each of the other dose levels will also be presented, without calculation of confidence intervals.

Exploratory Analysis

An exploratory analysis will be conducted to investigate the relationship of changes in the levels of the biomarkers brain natriuretic peptide (BNP) and troponin I to the frequency of specific AEs and the occurrence of DLT. Additionally, the benefit, if any, of using these measures in addition to routine monitoring by ECG and echocardiogram will be explored. The frequency of conversion in immunofixation results from positive to negative will be explored and the disappearance of free light chain. Efficacy at additional doses may be explored for potential use in future Phase II clinical trials.

Interim Analysis

Interim analyses will be performed following each cohort during the Phase I portion of the study. No interim analysis is planned for the Phase II portion.

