5.2.1 Inclusion Criteria

Subjects must meet the following inclusion/exclusion criteria to be eligible for the study.

Inclusion criteria

- 1. Understand and voluntarily sign an informed consent form.
- 2. Age ≥ 18 years at the time of signing the informed consent form.
- 3. Able to adhere to the study visit schedule and other protocol requirements.
- 4. Biopsy proven tissue amyloid deposits or positive fat aspirate
- 5. Proof of AL type (either a or b suffices)
- 6. Measurable plasma cell dyscrasia (a or b) AND c of the following required:
 - a. Monoclonal protein in the serum or urine by immunofixation electrophoresis
 - b. Plasmacytosis of bone marrow (< 30% plasma cells) with monoclonal staining for kappa or lambda light-chain isotype

- c. dFLC \geq 50 mg/L (dFLC=difference in involved and uninvolved serum free light-chain levels)
- 7. Must have received ≥ 1 prior treatment for AL amyloidosis, if it is intensive chemotherapy and an autotransplant it must be at least 3-6 months prior to enrollment on this study
- 8. Subjects must have recovered from the reversible side effects of any prior therapy; permanent and stable side effects/changes are acceptable. Prior treatment for AL amyloidosis with chemotherapy, thalidomide, lenalidomide or steroids is not an exclusion.
- 9. SWOG performance status of ≤ 2 at study entry (see Appendix 2).
- 10. Laboratory test results within these ranges:
 - d. Neutrophil $\geq 1.5 \text{ x}10\text{e}9/\text{L};$
 - e. Platelets $\geq 100 \times 10e9/L$;
 - f. Total bilirubin $\leq 1.5 \text{ mg/dL}$
 - g. AST (SGOT) and ALT (SGPT) \leq 2 x ULN
 - h. Serum creatinine $\leq 3.0 \text{ mg/dL}$
- 11. Disease free of prior malignancies for ≥ 5 years with exception of currently treated basal cell, squamous cell carcinoma of the skin, or carcinoma "in-situ" of the cervix or breast.

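### Section 10.3 gives organ response the precision of 6 of 18, but the design does not ensure that all 18 MTD subjects have an organ that section 7.2 can score

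*Combined protocol and SAP*

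**What the plan says.** Section 10.3 (Determination of Sample Size) takes 18 subjects as the basis for precision: "6 patients will be dosed at the MTD during the phase I portion of this trial plus the additional 12 patients at this MTD dose". It works an example of 6 responders in 18, "Using the adjusted Wald's confidence interval for the proportion and the corresponding point estimates for hypothetical data", and reports an estimate of 35.57% "with a 90% confidence interval between 18.21% and 52.81% with similar estimates for organ response". No separate denominator for organ response appears anywhere. For the analysis itself, 10.3 says: "The analysis of response data at the MTD will be descriptive, consisting of 2-sided 90% confidence intervals".

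Section 7.2 gives organ-response criteria for kidney, heart and liver only. For nerve involvement, "organ response will be indeterminable for subjects in which neurotoxicity is the only site of organ involvement". For the gut, "organ response will be indeterminable for subjects in which GI is the only site of organ involvement". It calls each of these sites inadequate for assessing response, so a subject with nerve plus GI involvement and nothing else has no scoring route either.

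Section 5.2.1 (item 4) asks for "Biopsy proven tissue amyloid deposits or positive fat aspirate". The measurable-disease criterion (item 6) concerns the clone and a dFLC of at least 50 mg/L. Nothing in 5.2.1 or 5.2.2 requires kidney, heart or liver involvement.

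Section 10.2 lists, among the data for the organ-response endpoint, "orthostatic vital signs and symptoms, GI symptoms and evaluation of peripheral neuropathy".

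Three general rules in 10.3 also bear on the denominator: missing values are not imputed, category percentages are taken over non-missing values, and the efficacy population is the 12 expansion subjects.

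**The concern.** Entry guarantees that hematologic disease can be measured, through the dFLC threshold. It guarantees nothing comparable for organs. The organ-response precision therefore rests on a count of 18 that the entry criteria do not secure.

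The plan also creates a category, indeterminable, and does not say how the analysis counts it. The nearest rule is the one on non-missing values, which suggests dropping these subjects. Applied literally, it would also drop a subject with a scorable organ who dies or leaves before any later organ assessment. Such subjects cannot be shown to have responded, so leaving them out can inflate the rate.

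At stake is a named secondary endpoint with its own 90% interval. Section 10.1 plans an informal comparison of responses with lenalidomide plus dexamethasone, and a reader of that comparison needs to know the denominator.

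**Working it through.** **Inputs.** Two-sided 90% level, so z = 1.645 and z² = 2.706; adjusted Wald method; n = 18; 6 responders (all from 10.3). The number of unscorable subjects is not in the documents. I assume 0, 3 or 6 of 18.

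**Formula.** p̃ = (x + z²/2) / (n + z²); interval = p̃ ± z·√[p̃(1 − p̃)/(n + z²)].

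**Step 1: reproduce the plan's figure.** For 6 of 18, p̃ = (6 + 1.353)/(18 + 2.706) = 7.353/20.706 = 35.51%. Half-width = 1.645 × √(0.3551 × 0.6449/20.706) = 17.3 points. The interval is 18.21% to 52.81%, so both limits match. The printed point estimate of 35.57% does not: the formula gives 35.51%, which is also the midpoint of the printed limits, (18.21 + 52.81)/2. This looks like a slip and has no bearing on the point.

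**Step 2: same method and same crude rate of one third, scorable subjects only.**

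| Unscorable (assumed) | Responders / scorable | Adjusted estimate | 90% interval | Half-width (points) |
|---|---|---|---|---|
| 0 | 6/18 | 35.51% | 18.21% to 52.81% | 17.3 |
| 3 | 5/15 | 35.88% | 17.13% to 54.63% | 18.8 |
| 6 | 4/12 | 36.40% | 15.76% to 57.04% | 20.6 |

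**Step 3: same data, unscorable subjects kept in as non-responders.** With 5 responders and 3 unscorable, the crude rate is 5/15 = 33.3% if they are dropped and 5/18 = 27.8% if kept (adjusted 30.68%, interval 14.01% to 47.35%). With 4 responders and 6 unscorable, it is 4/12 = 33.3% or 4/18 = 22.2% (adjusted 25.85%, interval 10.03% to 41.68%). In these two cases the choice of denominator moves the crude rate by about 6 and 11 points.

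**Step 4: scorable subjects with no later assessment.** As an illustration, take 15 scorable subjects, 5 responders and 3 never reassessed. The non-missing rule gives 5/12 = 41.7%. Counting the 3 as non-responders gives 5/15 = 33.3%, a difference of 8.3 points. The figure of 3 is assumed.

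**Step 5: the other denominator in 10.3.** If the 12-subject efficacy population is used instead of 18, a one-third rate already gives 4/12, or 15.8% to 57.0%, before any subject is unscorable.

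**The case against.** The strongest reply is that little is lost. The plan says similar, not identical, and describes its data as hypothetical. With 3 of 18 unscorable the half-width rises by only about 1.5 points, which a reasonable person could still call similar. No share of unscorable subjects is documented and it may be zero. The endpoint is secondary and descriptive, and no test, sample size or stopping rule uses its denominator. Sections 7.2 and 10.3 read together already lean towards excluding indeterminable subjects. All of this stands and limits the size of the point. It does not supply the missing rule or make 18 a secured count.

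Three stronger readings are tempting, and the documents do not support them:

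- A reader might infer that the hematologic rate uses all treated subjects, so that the two rates would sit side by side on different bases. Section 10.3 does not say so. It names a 12-subject efficacy population, and its non-missing rule applies to hematologic categories as well.
- A reader might infer from 10.2 that nerve and GI findings will be scored as organ response. Section 7.2 rules that out, and 10.2 lists data without setting scoring rules. These items may serve to record involvement or worsening: 10.3 plans an analysis of time to worsening of organ function, and 7.2 denies response if criteria in section 10.4 are met. Those criteria are not there, since 10.4 is the safety evaluation. Deleting the items could remove inputs that are needed.
- A reader might quote a large shift, such as 6/18 = 33.3% against 6/12 = 50.0%. That takes one third as unscorable and holds all 6 responders fixed. It is an extreme of an assumed range, not a finding about this trial.

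**Conclusion.** The point holds in a limited form. The organ-response precision in 10.3 is right only if every one of the 18 MTD subjects has kidney, heart or liver involvement, and the entry criteria do not ensure that. The effect on precision is modest: at a one-third rate the half-width goes from 17.3 points to 18.8 with 15 scorable and 20.6 with 12. Those shares are assumptions. The more practical weakness is the open denominator. The rule on non-missing values can raise the rate by dropping scorable subjects who were never reassessed, and nothing says how indeterminable subjects are reported. The mismatch between 10.2 and 7.2 is one of labelling. It should be corrected, but it does not show that unscorable sites will be scored. The change is worth making before the response analysis; the primary objective is unaffected.

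**What to change.** - **7.2:** define an organ-evaluable set: MTD subjects with kidney, heart or liver involvement at baseline, with involvement itself defined.
- **10.3, precision:** replace the clause that extends the 6-of-18 estimate to organ response with the precision for this set over a range of sizes, for example 6/18 (18.2% to 52.8%), 5/15 (17.1% to 54.6%) and 4/12 (15.8% to 57.0%).
- **10.3, missing data:** state, as an explicit exception to the non-missing rule, that evaluable subjects without a later organ assessment count as non-responders. Report alongside the number indeterminable and the rate on all MTD subjects.
- **10.3, populations:** reconcile the 18 subjects used for precision with the 12-subject efficacy population.
- **10.2:** keep the orthostatic, GI and neuropathy items, but label them as descriptive or for organ worsening and not for scoring organ response, to match 7.2.

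The cost is one new definition, edits to the precision, population and missing-data text, a relabelled list and an extra table row. No extra subjects are needed. The stated organ-response precision becomes slightly less favourable.
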